### ***6.2.2 Cabozantinib Dose Modifications, Interruptions and Discontinuation***

Subjects will be monitored for AEs from the time of signing informed consent until 30 days after the date of the last dose of cabozantinib. Any SAE that the Investigator believes to be related to cabozantinib or study procedures can be reported at any time after the last dose with no time limitation during the follow-up period. Subjects will be instructed to notify their physician immediately for any occurring AE and unscheduled safety visits are allowed at any time. Causality assessment of AEs should include at minimum confounding factors such as disease and concomitant medications. The severity of all AEs will be graded by the Investigator according to the CTCAE version 5.0.

The following should be taken into consideration in decisions regarding dose modifications (reductions or interruptions):

- As a general approach, all AEs should be managed with supportive care at the earliest signs of toxicity considered. Should this be ineffective, dose reductions or interruptions should be considered to prevent worsening of toxicity;
- The assigned dose for cabozantinib is 60 mg/day. Two reductions in dose levels of cabozantinib are permitted but these reductions must be incremental (see [Table 3](#));
- Dose modification criteria for cabozantinib are shown in [Table 4](#). Dose reductions and/or interruptions should be implemented for unacceptable toxicity. Doses may be modified at any time during the study;
- Dose modifications or interruptions may also occur in the setting of lower grade toxicity than that defined in [Table 4](#), if the Investigator feels it is in the interest of a subject's safety and will optimise drug tolerability;
- Interruption of cabozantinib treatment due to AEs may occur at any time per Investigator discretion. If study treatment is interrupted due to AEs for more than 6 weeks, cabozantinib should be discontinued;
- Dose interruptions for reason(s) other than AEs (e.g. surgical procedures) can be longer than 6 weeks but require Sponsor approval. The acceptable length of interruption will depend on agreement between Investigator and the Sponsor.

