**Table 3 Dose Reductions of Cabozantinib**

Assigned dose	First Dose Level Reduction	Second Dose Level Reduction
60 mg cabozantinib orally q.d.	40 mg cabozantinib orally q.d.	20 mg cabozantinib orally q.d.

Abbreviations: q.d. = Once daily

Cabozantinib should be discontinued if a dose of 20 mg q.d. (minimum dose) is not tolerated

Table 4 Dose Modifications of Cabozantinib for Treatment-related AEs

Common Terminology Criteria for Adverse Events (CTCAE) version 5.0 Grade	Recommended Guidelines for Management a
Grade 1 AEs	Add supportive care as indicated. Continue cabozantinib treatment at the current dose level if AE is manageable and tolerable.
Grade 2 AEs which are tolerable and are easily managed	Continue cabozantinib treatment at the current dose level with supportive care.
Grade 2 AEs which are intolerable and cannot be adequately managed	At the discretion of the Investigator, cabozantinib should be dose reduced or interrupted. Note: It is recommended that dose holds be as brief as possible.
Grade 3 AEs (except clinically non-relevant laboratory abnormalities)	Cabozantinib must be interrupted until the adverse reaction resolves to Grade $\leq 1$ . Note: It is recommended that dose holds be as brief as possible.
Grade 4 AEs (except clinically non-relevant laboratory abnormalities)	Subjects should have cabozantinib interrupted immediately. Discontinue cabozantinib unless the following criteria are met: 
 
• Subject is deriving clear clinical benefit as determined by the Investigator;
 
• Toxicity can be managed with a dose reduction following recovery to Grade 1 (or baseline) and optimal medical care.
 

Abbreviations: AE = Adverse event.

Note: The dose delay and modification criteria for specific medical conditions are provided in [Section 6.2.4](#). For reinstatement of cabozantinib after dose interruption, please see [Section 6.2.3](#).

a Dose adjustment is only needed if toxicity is considered to be related or has an unclear relationship to cabozantinib treatment.

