### 6.2.3 Cabozantinib Dose Reinstatement and Reescalation

If toxicity decreases to CTCAE version 5.0 Grade  $\leq 1$  or to baseline values (or lower) and is considered to be unrelated to study treatment, then subjects may restart cabozantinib with no dose change.

If toxicity decreases to CTCAE version 5.0 Grade  $\leq 1$  or to baseline values (or lower) and is considered to be possibly related to study treatment, then subjects may restart cabozantinib at a reduced dose (see [Table 3](#) for dose reduction schedule).

Subjects receiving a dose of 20 mg q.d. may be restarted at the same dose if deemed safe at the discretion of the Investigator. Subjects unable to tolerate a dose of 20 mg q.d. should discontinue study treatment.

Re-escalation to the previous dose (but not higher than 60 mg/day) may be allowed at the discretion of the Investigator but no sooner than 2 weeks beyond resolution of the AEs that led to dose reduction. Dose re-escalation is not allowed for a drug-related dose reduction triggered by myelosuppression or by Grade 4 AEs affecting major organs (e.g. central nervous system (CNS), cardiac, hepatic, renal).

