## 8 OSTEONECROSIS

Osteonecrosis has been reported in subjects treated with cabozantinib. Additional risk factors include use of bisphosphonates and denosumab, chemotherapy and anti-angiogenic drugs, use of corticosteroids, local radiotherapy, and dental or orofacial surgery procedures.

Osteonecrosis of the jaw (ONJ) can manifest as jaw pain, osteomyelitis, osteitis, bone erosion, tooth or periodontal infection, toothache, gingival ulceration, or gingival erosion. Persistent pain or slow healing of the mouth or jaw after dental surgery may also be manifestations of ONJ.

Perform an oral examination prior to initiation of cabozantinib and periodically during cabozantinib therapy. Advise subjects regarding oral hygiene practice and to quickly report symptoms to the Investigator. Caution should be used in subjects receiving bisphosphonates.

Invasive dental procedures should be avoided. In cases where dental procedures are unavoidable, treatment with cabozantinib should be held for at least 4 weeks prior to the procedure and resumed after complete wound healing has occurred. Bone healing may often require a protracted time.

If ONJ occurs, cabozantinib treatment should be held and should not be restarted until the condition has sufficiently healed and the Sponsor has approved the re-initiation of therapy.

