
A frequency table of the number and percentage of subjects will be provided for all / active medical and surgical history by primary system organ class and preferred term for each cohort and overall, for the safety population (Table 14.1.16).

3.2.9 *Subject compliance*

A listing will be presented for drug administration (dose, quantity, date, reason for change) by subject for each cohort (Listing 16.2.5.1), and for drug dispensation and compliance (Listings 16.2.5.2 and 16.2.5.3). Deviations from number of tablets and dosage taken and scheduled intake will be presented.

A summary table of compliance expressed in percentage and by category (<80% / >120%) will be produced by cohort and overall, for the safety population (Table 14.1.17). The compliance will be calculated as the number of tablets taken divided by the number of tablets planned to be taken multiplied by 100 (see Appendix 1 (23)).

SAP Final: Version 6.0: 17 August 2023

Summary tables of study drug dose reduction and interruption are planned in Section 3.2.4. Summary tables of AEs leading to dose modification are also planned in Section 3.2.2.1.

3.2.10 *Prior and concomitant therapies*

Prior and ongoing medications started before the study and concomitant medications will be coded using World Health Organization Drug Dictionary (WHODD) most recent version. The therapeutic class will correspond to the second level of Anatomic Therapeutic Class (ATC) code, that is, corresponding to the first 3 figures.

Medication start and stop dates will be compared to the date of first dose of study medication to allow medications to be classified as either Prior only, both Prior and Concomitant, or Concomitant only. Medications starting after the last dose of study drug will be listed but will not be classified or summarized.

Medications that start and stop prior to the date of first dose of study medication will be classified as Prior only. If a medication starts before the date of first dose of study medication and stops on or after the date of first dose of study medication, then the medication will be classified as both Prior and Concomitant. Medications will be classified as Concomitant only if they have a start date on or after the date of first dose of study medication.

If medication start and/or stop dates are missing or partial, the rules mentioned in Section 3.2.3.2 will be applied, and the algorithm for imputation is defined in Appendix 1 (16).

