In case of missing screening day, the day will be imputed to 15. In case of missing screening month, the month will not be imputed.

In the same way, in case of missing diagnosis day, the day will be imputed to 15. In case of missing diagnosis month, the day and month will be imputed to 01JUL. No imputation will be performed for missing year.

SAP Final: Version 6.0: 17 August 2023

(18) Treatment duration on 1st anti-cancer therapy

Treatment duration on 1st anti-cancer therapy will be calculated as (latest stop date – earliest start date)+1. It will be then divided by 30.4375 to be presented in months.

In case of missing drug start day, the day will be imputed to 15. In case of missing drug start month, the month will not be imputed.

In the same way, in case of missing drug stop day, the day will be imputed to 15. In case of missing drug stop month, the month will not be imputed.

No imputation will be performed for missing year.

In case, the duration treatment cannot be derived as <6 months, or ≥ 6 months based on the available data, the subgroup ≥ 6 months will be considered by default.

(19) Study exposure

Study exposure will be calculated as:

Study exposure (days) = last visit attended – informed consent date +1. It will be then divided by 30.4375 to be presented in months.

(20) Study drug exposure

a) Total study drug exposure will be calculated as:

Total study drug exposure (days) = last study drug intake date – first study drug intake date +1. It will be then divided by 30.4375 to be presented in months.

b) Actual study drug exposure will exclude the study drug interruptions.

For interim analysis, the last attended visit date will be considered as the last study drug intake date, in case the subject has not ended the treatment prior to this visit.

(21) Average daily dose

Average daily dose in mg/day will be calculated as the number of tablets taken multiplied by the corresponding dosage in mg from each kit, and divided by the total study drug exposure in days (i.e. including the study drug interruptions).

(22) Age

Subject age (years) will be derived as (screening year – birth year).

(23) Compliance

The compliance will be calculated as :

Total number of tablets taken divided by Total number of tablets planned to be taken multiplied by 100.

Total number of tablets planned to be taken will be calculated as (last study drug intake date – first study drug intake date)+1, as the planned intake is one tablet per day.

(24) Study day

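### The SAP compliance formula counts instructed treatment holds as missed tablets, so a fully adherent patient can be reported below 80%

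*SAP*

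**What the plan says.** SAP Appendix 1, item (23), defines compliance as 100 times tablets taken over tablets planned. Tablets planned is the last intake date minus the first intake date, plus 1, and the reason given is "as the planned intake is one tablet per day". SAP Section 3.2.9 repeats the ratio and points to this item: "A summary table of compliance expressed in percentage and by category (<80% / >120%) will be produced by cohort and overall" (Table 14.1.17, safety population). The table is listed for both the final and the follow-up analysis. Neither place removes interruptions.

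The protocol builds in days without a dose, followed by restart:

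- Table 4, Grade 3 events: "Cabozantinib must be interrupted until the adverse reaction resolves to Grade" 1 or lower. Clinically non-relevant laboratory abnormalities are excepted, and adjustment applies only where the event is related or of unclear relationship. The table adds: "It is recommended that dose holds be as brief as possible".
- Section 6.2.2: "Interruption of cabozantinib treatment due to AEs may occur at any time per Investigator discretion". AE holds beyond 6 weeks should lead to discontinuation; holds for other reasons may run longer with Sponsor approval.
- Section 6.2.3: after recovery from a possibly related event, "subjects may restart cabozantinib at a reduced dose"; after an unrelated event, with no dose change.
- Appendix 4 section 8, where a dental procedure cannot be avoided: "treatment with cabozantinib should be held for at least 4 weeks prior to the procedure and resumed after complete wound healing has occurred".

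The SAP handles interruptions explicitly elsewhere in the same appendix. Item (20b) defines actual exposure with interruptions removed. Item (21) divides by the full span and states that interruptions are included. Item (23) says neither.

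**The concern.** On an instructed hold day no tablet is scheduled. Item (23) still counts one as planned, and because none is taken the day lowers the percentage exactly as a skipped dose would. Table 14.1.17 then cannot separate a patient who followed an instruction from one who did not take the drug, which is the purpose of a compliance table. A reader who sees a count in the below-80% row will naturally take it as non-adherence.

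Nor does the figure work as a separate dose-intensity measure. For a patient taking one 60 mg tablet on each dosing day, item (23) is simply the average daily dose of item (21) divided by 60 mg and expressed as a percentage.

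A smaller fault lies in the same premise. Protocol 6.2.1 allows, exceptionally, a 20 mg plus a 40 mg bottle in place of 60 mg during a stock shortage. Two tablets are then taken on a day counted as one, and the percentage is inflated.

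**Working it through.** The documents give no compliance figure to reproduce, so the formula is applied directly.

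**Inputs**

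- Planned tablets T = last intake − first intake + 1 (SAP Appendix 1, item 23).
- Hold days H: 42 days is the AE limit (6 weeks, Protocol 6.2.2). 28 days is the minimum dental hold before the procedure (Appendix 4 section 8). 7, 14 and 21 days are illustrations.
- Average treatment of 8 months (Protocol 3.6): 8 × 30.4375 = 243.5, about 244 days.
- Category limit of 80% (SAP 3.2.9).
- The patient takes every tablet on every day that is not a hold day.

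**Formula.** Compliance = 100 × (T − H)/T. With H = 0 it gives 100%, as intended. It is below 80% when T < 5H.

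**Longest span that still reads below 80% with perfect adherence**

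| Hold (days) | Longest span (days) | Reading | One day longer |
|---|---|---|---|
| 7 | 34 | 27/34 = 79.4% | 28/35 = 80.0% |
| 14 | 69 | 55/69 = 79.7% | 56/70 = 80.0% |
| 21 | 104 | 83/104 = 79.8% | 84/105 = 80.0% |
| 28 | 139 | 111/139 = 79.9% | 112/140 = 80.0% |
| 42 | 209 | 167/209 = 79.9% | 168/210 = 80.0% |

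**At about 244 days**

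- 14 days held: 230/244 = 94.3%
- 28 days: 216/244 = 88.5%
- 42 days: 202/244 = 82.8%
- 48 days: 196/244 = 80.3%
- 49 days: 195/244 = 79.9%
- two 28-day holds: 188/244 = 77.0%

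No single hold of up to 42 days changes the category at this duration; accumulated holds do from 49 days.

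**Two patients, 200-day span, 158 tablets each.** One had a documented 42-day hold; the other skipped 42 days.

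- Item (23): 158/200 = 79.0% for both.
- Documented hold removed from the denominator: 158/158 = 100% for the first, 158/200 = 79.0% for the second.

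**Shortage dosing, 244 days, no holds**

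- 30 two-tablet days: 274/244 = 112.3%
- 49 days: 293/244 = 120.1%
- 60 days: 304/244 = 124.6%
- 60 such days with misses spread evenly: a true 70% reads 0.70 × 304/244 = 87.2%

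**The case against.** The strongest reply is that item (23) is a stated choice: intake against a full daily regimen, with its reason given, over the same span that item (21) uses. The SAP never calls the below-80% group non-adherent. Other outputs also supply context. Section 3.2.9 plans a drug administration listing with the reason for each change, and says "Deviations from number of tablets and dosage taken and scheduled intake will be presented". Tables 14.1.6 and 14.1.7 report exposure and interruptions, and AEs leading to dose modification are tabulated. A reader who consults all of these can tell the two example patients apart.

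That reduces the harm but does not repair the table. Item (21) declares that interruptions are included; item (23) does not, and it appears under the heading of subject compliance. None of the other outputs changes the percentage or its category.

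Two further objections stand as limits. First, the trigger is narrow: Table 4 has exceptions and asks for short holds, dental procedures are to be avoided in the first place, and at the expected average duration a single AE hold within 6 weeks does not cross 80%. Second, no consequence beyond the table is shown. The 80% major-deviation limit in Protocol 6.5 refers to the scheduled amount, and nothing in the documents says item (23) is used to apply it. The shortage scenario is exceptional and secondary.

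**Conclusion.** The concern holds, at minor severity. As written, item (23) scores instructed no-dose days followed by a restart as missed tablets, and a fully adherent patient falls below 80% when the span is under five times the hold. This occurs mainly with shorter treatment, repeated holds, or a long Sponsor-approved interruption.

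A hold that ends in discontinuation has no effect, because the span stops at the last intake. The calculations assume perfect intake on all other days. The documents give no frequency of holds or shortages, so the number of patients affected is unknown. The effect is confined to descriptive Table 14.1.17; the primary ORR test is untouched.

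**What to change.** In item (23), define planned tablets as the sum of the amount scheduled on each day from first to last intake. Using mg by kit strength, as item (21) already does, also removes the shortage distortion. Leave out only documented interruptions that the protocol or the Investigator directed or the Sponsor approved, identified from the eCRF dose intervals and reasons. Keep no-dose periods due to the patient's own non-adherence in the denominator, so that the change does not hide them.

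Footnote the denominator in Table 14.1.17 and keep average daily dose as the separate dose-intensity measure. If the same percentage is used for the 80% limit in Protocol 6.5, apply the same definition there. No dosing or hold rule needs to change.

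The cost is derivation text and programming. Protocol 6.5 says the eCRF records constant-dose intervals, no-dose periods and the reason for a change. It also says the site's own compliance records are not entered directly, and the documents do not show the reason categories. Confirm before programming that these separate authorised holds from the patient's own.

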#### 6.2.1 *Administration of Cabozantinib*

Cabozantinib tablets are meant to be taken orally only and cannot be crushed for dissolving in liquid or administered through other routes including percutaneous endoscopic gastrostomy (PEG) tubes. Cabozantinib tablets should not be administered to subjects who do not have adequate swallowing capacity. This product cannot be taken with food, thus subjects must not eat 2 hours before and 1 hour after taking cabozantinib.

The date of the first dose of cabozantinib is defined as baseline (Day 1, Visit 2). Subjects will take cabozantinib tablets q.d. at home, at the same time each day, preferably at bedtime. Any unused study treatment must be returned to the investigational site for drug accountability and disposal. If a dose is missed, the missed dose should not be taken less than 12 hours before the next one.

The recommended dose is 60 mg q.d. as indicated in all approvals of cabozantinib (Cabometyx™). A dose of 60 mg should be maintained in the absence of treatment-emergent toxicity; however, management of suspected adverse drug reactions may require temporary interruption and/or dose reduction of cabozantinib therapy (see [Table 4](#)). When dose reduction is necessary, it is recommended to reduce to 40 mg q.d. and then to 20 mg q.d. Dose interruptions are recommended for management of CTCAE Grade 3 or greater toxicities or

intolerable Grade 2 toxicities. Dose reductions are recommended for events that, if persistent, could become serious or intolerable (see [Section 6.2.2](#)).

The Sponsor will provide each Investigator with adequate supplies of cabozantinib bottles (30 tablets each), which will be supplied as 60 mg, 40 mg and 20 mg yellow film-coated tablets. The 60 mg tablets are oval, the 40 mg tablets are triangle shaped and the 20 mg tablets are round.

Exceptionally, in case there is a stock shortage of 60 mg tablets, the Sponsor will dispense a mix of bottles of cabozantinib in lower dose (e.g. 1 bottle of 20 mg + 1 bottle of 40 mg instead of 1 bottle of 60 mg).

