## **6.5 Procedures for Monitoring Subject Compliance**

The Investigator will be responsible for monitoring subject compliance. Subjects may be withdrawn from the study at any time if the Investigator or Sponsor determines that the subject is not in compliance with the study protocol.

Administration compliance will be assessed at the investigational site using drug dispensing and return records, progress notes about dose reductions/holds and subject interview. These data will not be directly recorded in the eCRF; rather, the eCRF will capture intervals of constant dose and reasons for changes in dose level (e.g. a new record completed each time dose level changes, including periods where no dose was taken, and the reason for a dose level change).

Deviations below 80% of the scheduled amount of cabozantinib intake will be regarded as a major protocol deviation.

Where a subject is consistently noncompliant with cabozantinib intake they should be discontinued from study treatment/withdrawn from the study (see [Section 4.3](#)).

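### The compliance formula plans one tablet a day, so it reads too high on any days supplied as 20 mg + 40 mg tablets in place of one 60 mg tablet

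*SAP*

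**What the plan says.** SAP Appendix 1 (23) defines compliance as "Total number of tablets taken divided by Total number of tablets planned to be taken multiplied by 100". The denominator is a day count: "Total number of tablets planned to be taken will be calculated as (last study drug intake date – first study drug intake date)+1", justified "as the planned intake is one tablet per day". SAP 3.2.9 repeats the tablet ratio and sends the result to Table 14.1.17, a safety-population summary with classes below 80% and above 120%. The table is listed for both the final and the follow-up analysis (SAP Appendices 3 and 4).

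Protocol 6.2.1 supplies 60, 40 and 20 mg tablets in bottles of 30. It adds a contingency: "Exceptionally, in case there is a stock shortage of 60 mg tablets", lower strengths are dispensed together, for example "1 bottle of 20 mg + 1 bottle of 40 mg instead of 1 bottle of 60 mg".

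Protocol 6.5 has its own threshold: "Deviations below 80% of the scheduled amount of cabozantinib intake will be regarded as a major protocol deviation".

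The SAP's average daily dose, Appendix 1 (21), does weight each tablet by the strength of its kit. Compliance, item (23), does not.

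**The concern.** The numerator counts tablets of any strength, while the denominator allows one tablet for each calendar day. On a day supplied as 20 mg + 40 mg, a patient who takes exactly the intended 60 mg adds two tablets to the numerator and one to the denominator. The percentage is then wrong in two ways. A patient who takes every dose can be shown above 100%. The surplus tablets can also hide missed days, so that a patient who belongs in the class below 80% is tabulated outside it. At stake is whether Table 14.1.17 can be read as adherence for any patient who received the mix.

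**Working it through.** **Inputs**

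- Tablets taken over calendar days, one planned per day: SAP Appendix 1 (23) and 3.2.9.
- Two tablets per day on the mix, 30 tablets per bottle, so one bottle pair covers 30 days: Protocol 6.2.1.
- Treatment length: Protocol 3.6 expects an average of 8 months, and 8 × 30.4375 = 243.5 days. I use 240 days as a round figure and 90 days as a short-treatment illustration.
- Share of days on the mix: not given in the documents. It is treated as an assumption and shown over its range.

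**Formula.** Let D be the days from first to last intake, s the share of days supplied as the mix, and a the share of doses taken, with missed doses spread evenly over both kinds of day. Tablets taken = a × D × [(1 − s) + 2s] = a × D × (1 + s). Reported compliance = 100 × a × (1 + s).

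**The SAP's premise reproduced.** With s = 0 and a = 1 the formula gives 100%. This is correct at 60, 40 or 20 mg, since each dose level has its own single tablet.

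**Fully adherent patient (a = 1)**

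| Days on the mix | s | Reported |
|---|---|---|
| 30 of 240 | 0.125 | 270/240 = 112.5% |
| 60 of 240 | 0.25 | 300/240 = 125% |
| 30 of 90 | 0.333 | 120/90 = 133% |
| All days | 1 | 200% |

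The class above 120% requires 1 + s > 1.20, that is s > 0.20. A single 30-day pair does this only if 30/D > 0.20, so D < 150 days.

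**Missed doses hidden.** Take 240 days with one 30-day mix taken in full and 78 of the 210 single-tablet days missed.

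- Tablets taken: (210 − 78) + 2 × 30 = 132 + 60 = 192. Reported: 192/240 = 80%, which is not below 80%.
- Days dosed: 132 + 30 = 162. True adherence: 162/240 = 67.5%.

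If the misses are instead spread evenly, the adherence that reads 80% is 80/1.125 = 71.1%. With every day on the mix it is 80/2 = 40%.

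**Same patient under the two possible repairs**

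- Two tablets planned on mix days: 192/(210 + 60) = 192/270 = 71.1%.
- In mg at a prescribed 60 mg: (132 + 30) × 60 / (240 × 60) = 9,720/14,400 = 67.5%.

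Both return the patient to the class below 80%, and both give 100% for a fully adherent patient. Only the mg version recovers the day-based adherence, because the tablet version gives mix days double weight.

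**The case against.** The strongest objection is that the trigger may never have occurred. The protocol calls the mix exceptional, neither document says it was dispensed, and one tablet a day is right for every routine dose level. This stands, and it makes the point conditional. It does not supply the missing rule for a supply the protocol expressly allows.

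The second objection is that other outputs would reveal the problem. SAP 3.2.9 also presents deviations in tablets and dosage against the scheduled intake, with listings of regimen, dispensation and compliance. Average daily dose is in mg, and reductions and interruptions are tabulated. This stands in part: an odd percentage could be traced to its cause. But average daily dose alone cannot separate missed doses from reductions or holds, and none of these outputs corrects the percentage or the classes in Table 14.1.17.

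A reader might also infer more than the documents support:

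- *That adherent patients who receive the mix will generally be shown above 120%.* They will not. One bottle pair over 240 days gives 112.5%.
- *That the class above 120% denotes overdosing.* SAP 3.2.9 attaches no such label.
- *That the formula lets patients escape the 80% major deviation or a per-protocol exclusion.* Protocol 6.5 has sites assess compliance from dispensing and return records, notes on reductions and holds, and subject interview. SAP 2.1.3 and 2.1.4 place the exclusion criteria in the Protocol Deviation Specifications, which are not available here. No text says that item (23) or Table 14.1.17 decides either matter.
- *That Protocol 6.5 sets its limit in mg.* It refers to an amount and names no unit.

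**Conclusion.** The point holds as a conditional and minor one. SAP Appendix 1 (23) and Protocol 6.2.1 disagree on how many tablets are planned per day when the mix is supplied, and nothing else in the SAP reconciles them.

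The inflation factor is one plus the share of days on the mix, given evenly spread misses. For a fully adherent patient this runs from 112.5% (30 of 240 days) through 133% (30 of 90) to a maximum of 200%. That maximum is for the 20 mg + 40 mg example, and the protocol leaves other mixes open. In the other direction, 67.5% adherence can read 80%, though this case needs 78 missed single-tablet days and every mix tablet taken.

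The size in this trial rests on whether, and for how long, the mix was dispensed, which the documents do not say. The effect is confined to a descriptive table. No effect on the test of response rate, on the major-deviation decision or on the per-protocol set is shown.

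**What to change.** Keep the current day count and change one of two things in SAP Appendix 1 (23) and 3.2.9:

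- **Preferred:** compute mg taken (tablets times strength per kit, as item (21) already does) divided by the prescribed daily mg summed over the same calendar days, times 100.
- **Minimum:** count two planned tablets on each day supplied as the mix.

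Apply the existing classes, below 80% and above 120%, to the new figure. In the mg version, say which prescribed dose is carried on days within a treatment hold, so that holds enter the denominator as they do now. Whether they should is a separate matter and is left unchanged here.

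The cost is a wording change in two places and minor programming. Strength per kit is already needed for item (21), and Protocol 6.5 says the eCRF captures intervals of constant dose. If the dispensation records show that no mix was issued, a footnote to Table 14.1.17 saying so would be enough.
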